4.4 End of Study Definition

The end of the study is defined as the date of the final safety follow-up after the LPLV.

4.5 PRN1008 Administration

Part A: Initial PRN1008 dosing will be 400 mg *bid*. The maximum dose in this study, after dose adjustment, will be 600 mg *bid*. Clinical response and tolerability will be assessed at each visit. Dosing may be adjusted according to [Section 4.6](#).

Part B: Initial PRN1008 dosing will be 400 mg *qd*, unless patients previously initiated the study with a 12-week treatment period are on higher doses, in which case they will initially continue with their current dose level. The maximum dose in this study, after dose adjustment will be 600 mg *bid*. Clinical response and tolerability will be assessed at each visit. Dosing may be adjusted according to [Section 4.6](#).

PRN1008 tablets should be taken with a glass of water and may be taken with or without food, i.e., a period of fasting is not required.

4.5.1 Rationale for PRN1008 Dosage Selection

400 mg *bid* (Part A): The 400 mg *bid* starting dose is based upon the dose known to produce ~70% BTK occupancy at trough (~85% average occupancy over the day), as adjusted by results of the relative bioavailability study, where the tablet had ~70% of the exposure of the equal dose of the liquid formulation. Adequate BTK occupancies with 400 mg *bid* dosing of the IR tablet has been confirmed in nearly all of the 21 patients with pemphigus studied to date. To confirm achievement of target, BTK occupancy measurements after the first dose will be expeditiously processed and provided to the treating physician in time for a follow-up visit at Day 15 (**Part A** only). This dose level has adequate safety factors to exposures in chronic toxicology studies ([Section 1.3](#)).

400 mg *qd* (Part B): In some but not all animal studies, a dose-response relationship between pre-dose BTK occupancy and clinical efficacy was observed. As it is unknown whether a once daily PRN1008 dose will provide adequate pharmacodynamic effect, a 400 mg *qd* dose is being tested in **Part B**, with the option to expeditiously dose-escalate to higher doses at or after the Week 3 visit. This dose level has adequate safety factors to exposures in chronic toxicology studies ([Section 1.3](#)).

Maximum dose of 600 mg *bid*: A dose level 50% higher than the target upper dose level of 400 mg *bid* was arbitrarily chosen based on previous clinical safety data in healthy volunteers at higher exposures and adequate safety factors to exposure in animal toxicology studies.

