1.3 Summary of PRN1008 Animal Toxicity Studies

1.3.1 13-week GLP Toxicology

In the 13-week repeat-dose GLP toxicity studies with PRN1008, doses of up to 500 mg/kg/day and 300 mg/kg/day were given to rats and dogs, respectively. The No Observed Adverse Effect Level (NOAEL) in rats was considered to be 150 mg/kg/day and the NOAEL for male dogs was 30 mg/kg/day. The NOAEL in female dogs is less than 30 mg/kg/day, based on body weight loss in one female administered 30 mg/kg/day. At doses above 150 mg/kg, the lungs of some rats showed increased macrophages and bronchoalveolar papillary hyperplasia. In dogs, PRN1008-related findings considered potentially PRN1008-related were observed in the liver and lymphoid tissues. At doses above 30 mg/kg in dogs, changes in liver function (mainly ALT and AST), loss of appetite, and associated weight loss were observed. These observations are considered clinically significant and their assessment in human subjects is included in the study procedures in this clinical protocol.

Orally administered PRN1008 did not affect the gross behavioral, physiological, or neurological state of rats at dose levels up to 500 mg/kg, and the NOAEL for effects on the cardiovascular and respiratory systems in dogs was considered to be 500 mg/kg.

PRN1008 tested negative in a battery of in vitro and in vivo genotoxicity studies.

1.3.2 6 and 9-month GLP Toxicology

In the 6-month rat oral GLP toxicology study, the no-observed-adverse-related level (NOAEL) was 50 mg/kg/day in females (AUC_{last} 5480 hr.ng/mL) and 150 mg/kg/day in males (AUC_{last} 5327 hr.ng/mL). The nature and severity of observed findings included lethality, decreased body weight gain, macroscopic and microscopic changes in the gastrointestinal tract, and neutrophilic inflammation in the brain. Adequate safety factors of ~4X are present to the rat NOAEL, assuming a maximum exposure in humans of 1360 ng.h/mL with a 600 mg bid dose, and 6X to the target exposure of 890 ng.h/mL with the 400 mg bid dose.

In the 9-month dog oral GLP toxicology study, the NOAEL for male and female animals was 30 mg/kg/day (AUC_{last} 963 hr.ng/mL), based on body weight loss that required food supplementation and the euthanasia of one male dog dosed at 50mg/kg/day. The observed findings in the dog of appetite decrease, weight loss, and reversible changes in liver function are readily monitorable in human studies.

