2.2 Selection of the Starting Clinical Dose of PRN1008 in Pemphigus

400 mg bid (Part A): The 400 mg *bid* starting dose is based upon the dose known to produce ~70% BTK occupancy at trough (~85% average occupancy over the day), as adjusted by results of the relative bioavailability study, where the tablet had ~70% of the exposure of the equal dose of the liquid formulation. Adequate BTK occupancies with 400 mg bid dosing of the IR tablet has been confirmed in nearly all of the 21 patients with pemphigus studied to date. To confirm achievement of target, BTK occupancy measurements after the first dose will be expeditiously processed and provided to the treating physician in time for a follow-up visit at Day 15 (**Part A** only). This dose level has adequate safety factors to exposures in chronic toxicology studies ([Section 1.3](#)).

400 mg qd (Part B): In some but not all animal studies, a dose-response relationship between pre-dose BTK occupancy and clinical efficacy was observed. As it is unknown whether a once daily PRN1008 dose will provide adequate pharmacodynamics effect, a 400 mg qd dose is being tested in **Part B**, with the option to expeditiously dose-escalate to higher doses at or after the Week 3 visit. This dose level has adequate safety factors to exposures in chronic toxicology studies ([Section 1.3](#)).

Please refer to [Investigator Brochure](#), Section 5.5.3, for additional information.

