9.3. Vital Sign Measurements

Summary tables presenting observed values and changes from baseline will be provided overall for vital sign measurements, which including systolic blood pressure (mmHg), diastolic blood pressure (mmHg), heart rate (bpm), respiratory rate (bpm), and temperature (°C). All vital sign measurements will be presented in a listing by patient and visit for Safety Population.

Systolic blood pressure values <90 or >140 mmHg or diastolic blood pressure values <60 or >80 mmHg will be flagged as outside the normal range. Resting heart rate <40 or >100 beats per minute will be flagged as abnormal. The number and percentage of patients for each normality category will be summarized overall at each visit.

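### The protocol's dog no-effect exposure gives a margin of 0.71 at 600 mg bid and 1.08 at 400 mg bid, which its general statements of adequate safety factors leave out, and Part A requires no summary of weight change

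*Protocol*

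**What the plan says.** Protocol section 1.3.2 compares human exposure with the 6-month rat study, "assuming a maximum exposure in humans of 1360 ng.h/mL with a 600 mg bid dose", and reports a factor of about 4. For the lower regimen it gives "6X to the target exposure of 890 ng.h/mL with the 400 mg bid dose". Both factors are expressly to the rat NOAEL. The next paragraph reports the 9-month dog study, where the NOAEL exposure was "963 hr.ng/mL), based on body weight loss that required food supplementation and the euthanasia of one male dog dosed at 50mg/kg/day". It gives no exposure multiple for the dog and says instead that the dog findings can be monitored in people.

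The later rationale sections are not limited to the rat. For 400 mg bid, and again for 400 mg qd, sections 2.2 and 4.5.1 say: "This dose level has adequate safety factors to exposures in chronic toxicology studies". For 600 mg bid, section 4.5.1 relies on healthy-volunteer safety data at higher exposures together with "adequate safety factors to exposure in animal toxicology studies". The risk-benefit text in section 2.3 mentions no dog margin.

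On reporting, Part A SAP section 9.3 says that summary tables of "observed values and changes from baseline will be provided overall for vital sign measurements" and then names five: systolic and diastolic pressure, heart rate, respiratory rate and temperature. Body weight is not among them. Part B SAP section 5.5.3 groups body weight with the vital signs and summarises actual values and change from baseline at each visit.

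**The concern.** A reader of sections 2.2 and 4.5.1 would take it that the exposure margins are comfortable in the animal studies as a group. The protocol's figures show that this is so in the rat but not in the dog, whose no-effect exposure is much lower. At the maximum dose, the human exposure that the protocol assumes is above the dog no-effect exposure. What is at stake is whether a safety property used to support the highest dose is stated correctly.

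The second part follows from the first. If the protocol's answer to the dog findings is monitoring rather than margin, the monitored quantity should be reported in summary form. In Part A, where the starting dose is 400 mg bid, nothing requires that for weight after baseline.

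**Working it through.** **Inputs, all from Protocol section 1.3.2 (AUC in hr.ng/mL).** Rat NOAEL exposure: 5480 (females), 5327 (males). Dog NOAEL exposure: 963 (both sexes). Human exposure: 1360 at 600 mg bid, 890 at 400 mg bid.

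**Formula.** Margin = animal AUC at the NOAEL / human AUC.

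| Study | AUC at NOAEL | Divided by 1360 (600 mg bid) | Divided by 890 (400 mg bid) |
|---|---|---|---|
| Rat, 6 months, female | 5480 | 4.03 | 6.16 |
| Rat, 6 months, male | 5327 | 3.92 | 5.99 |
| Dog, 9 months, both sexes | 963 | 0.71 | 1.08 |

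The rat rows reproduce the protocol's factors of about 4 and 6, so this is the calculation that the authors used. The dog row applies it to the figure that they printed but did not divide.

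**Reading the dog row.** At 600 mg bid, 1360/963 = 1.41, so the assumed human exposure is 41% above the dog no-effect exposure. At 400 mg bid, 890/963 = 0.92, so it is about 8% below.

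**Basis of the human figures.** 1360/890 = 1.53, close to the dose ratio 600/400 = 1.5, so the two human figures are on a common basis. The protocol does not state the interval; its rat ratios imply the same daily basis as the animal AUCs. If the human figures covered only 12 hours, the dog margins would be 963/2720 = 0.35 and 963/1780 = 0.54, which is less favourable.

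**400 mg qd.** No human AUC is given. If it were 40% to 60% of the 400 mg bid value (an assumption), the dog margin would run from 963/356 = 2.7 to 963/534 = 1.8, and would be 963/445 = 2.2 at one half.

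**Weight in Part A, place by place.**
- Schedule of assessments (Protocol Appendix 4; Part A SAP 15.1): weight at screening, on Day 1 before dosing, and at every visit from Day 15. Protocol section 8.1 lists weight under screening only, but the schedule collects it throughout.
- Part A SAP 6.1 and Table 14.1.2.1: baseline weight is tabulated.
- Listing 16.2.6.7: weight appears by visit, patient by patient.
- Part A SAP 9.3: five named parameters, without weight.
- Table 14.3.4.1: the shell has a generic parameter and draws on the listing that contains weight. Weight could be included, but nothing requires it.
- Part B SAP 5.5.3 and Table B.14.3.6.1: weight and its change are tabulated by visit.

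**The case against.** The best defence is that section 1.3.2 contains no arithmetic error. Its factors are labelled as rat factors, both reproduce, and the dog AUC is printed openly in the next paragraph with a stated answer, monitoring. That stands: the fault lies in the general wording of the later sections, not in a calculation.

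The choice of 600 mg bid also does not rest on animal data alone. Section 4.5.1 calls the 50% step arbitrary and cites healthy-volunteer data; section 1.4 describes 10 days of liquid dosing equivalent to 648 mg of tablet twice daily. That is real support, but it is short, and neither it nor monitoring is an exposure margin to a 9-month study. At 400 mg bid the ratio is above 1, and the documents set no threshold for adequacy, so there the statement is thinly supported rather than contradicted.

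On weight, Protocol section 11.10 already asks for change from baseline in quantitative safety data where appropriate. A listing of up to 25 patients can be read by eye. Part A also tabulates appetite score, liver tests and adverse events. These points reduce the gap but do not close it.

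A reader might infer more than the documents support:
- **That every dose lacks margin.** No AUC is given for 400 mg qd, so nothing is shown for it.
- **That the chronic-study statement is contradicted by the 0.71.** That sentence covers 400 mg bid and 400 mg qd; the 600 mg bid sentence refers to animal toxicology generally.
- **That sections 1.3.1 and 1.3.2 conflict over the dog NOAEL.** The 13-week and 9-month studies are separate and may give different limits.
- **That weight loss alone set the dog limit.** The euthanasia of one male at 50 mg/kg/day is cited as well.
- **That the 24-week extension, or an ethics committee's approval, rested on the factor.** Section 2.3 cites the observed safety and efficacy profile, and no passage documents such reliance.
- **That Part A does not report weight.** It tabulates baseline weight and lists weight by visit; only a required summary of post-baseline change is missing.

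**Conclusion.** The point holds, as a should-fix. On the protocol's own figures and method, the margin to the 9-month dog NOAEL is 0.71 at 600 mg bid and 1.08 at 400 mg bid, against about 4 and 6 in the rat. The statement for 600 mg bid, which names no species, is wrong as written; the one for 400 mg bid omits that the dog margin is close to 1. Both ratios assume that human and animal AUCs are on the same daily basis. This shows that the safety basis is described incompletely. It does not show that any dose is unsafe, and it changes no endpoint or estimate. The missing weight-change summary in Part A is a supporting point: small in itself, but relevant because monitoring is the protocol's stated answer to the dog findings.

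**What to change.** (a) In Protocol section 1.3.2, state the dog margin beside the rat margin for 600 mg bid and 400 mg bid, with the AUC interval. Reconcile the adequacy statements in sections 2.2 and 4.5.1, and the risk-benefit text in section 2.3, with it. One way is to limit the adequacy wording to the rat and say that the dog findings are handled by monitoring. For 400 mg qd, either give a human AUC or say that no margin has been calculated. No dose is proposed here.

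(b) In Part A SAP section 9.3 and Table 14.3.4.1, name body weight and summarise actual values and change from baseline by visit, as Part B SAP 5.5.3 does.

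The cost is a text amendment, which makes the stated margin less favourable, and one added parameter in an existing table. The schedule already collects the weights.

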4.5.2 Concomitant Medications

- Other immunosuppressive medications are not permitted except for low-dose corticosteroids and when rescue immunotherapy is triggered.
- Inducers and inhibitors of Cytochrome P450 3A (CYP3A) should be avoided as they may reduce or increase the exposure of PRN1008 ([Appendix 2](#)) when administered concomitantly.

- PRN1008 is a moderate CYP3A inhibitor and can increase the exposure of drugs metabolized by CYP3A when administered concomitantly. Narrow therapeutic index CYP3A substrate drugs should be avoided ([Appendix 3](#)) and care should be taken with other drugs metabolized by the CYP3A.
- Clinically relevant 3A substrate drugs (e.g. “sensitive substrate” listed in [Appendix 3](#)) should be managed by administering PRN1008 on a time schedule such that CYP3A substrate drugs can be given 2 hours or more after PRN1008.
- Acid reducing drugs may reduce the bioavailability of PRN1008 tablets. Therefore, PRN1008 should be administered 2 hours or more prior to such drugs. Proton pump inhibitors are not permitted during the study.

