1.5.1 Pharmacokinetics in Healthy Volunteers

With multiple dosing, the terminal half-life of PRN1008 is approximately 3 to 4 hours and the time of maximum concentration (T_{max}) at therapeutic multiple doses of 1.5 to 2.0 hours. With 300 mg *bid* of the liquid formulation, the accumulation ratio was 1.8 after 10 days of dosing. There is no effect of food on the AUC or C_{max} of the tablet formulation although the T_{max} is slightly delayed from 1.5 hours to approximately 2.5 hours. The volume of distribution is high (on the order of 2500 L) and plasma protein binding is 98% ([PRN1008 Investigators' Brochure](#)).

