2.4 Drug-Drug Interaction Potential

Based on in vitro data, CYP3A4 appears to be the major CYP isoform responsible for PRN1008 metabolism, including first-pass metabolism through the intestinal wall and liver. Therefore, PRN1008 plasma exposures have the potential to be altered if co-administered with other agents which either inhibit or induce CYP3A, however this potential interaction has not been studied clinically to date. Concomitant use of strong and moderate inducers of CYP3A should be avoided until their effects on PRN1008 exposure have been studied ([Appendix 2](#)).

A clinical drug-drug interaction study (PRN1008-002) was conducted to evaluate the effects of the liquid formulation of PRN1008 when administered simultaneously with midazolam, a probe CYP3A substrate. When co-administered with midazolam, midazolam plasma exposures increased approximately 3-fold. PRN1008 is therefore classified as a moderate inhibitor of CYP3A. As a result, sensitive CYP3A substrate drugs, particularly those with a narrow therapeutic index, should be avoided during treatment with PRN1008 ([Appendix 2](#)). Additional details are provided in the Investigator Brochure. PRN1008 does not appear to be an inducer of CYP isoenzymes.

Acid reducing drugs may reduce the bioavailability of PRN1008 tablets. Therefore, PRN1008 should be administered 2 hours or more prior to such drugs. Proton pump inhibitors are not permitted during the study (they resulted in a 50% decrease in PRN1008 tablet exposure when administered concomitantly in [Study PRN1008-006](#)).

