6.2 Exclusion Criteria

1. Previous use of a BTK inhibitor

*Patients enrolled in a previous version of this protocol who are still in their 12-week active treatment period with PRN1008 are eligible to continue treatment, initially with their current dose level, under this amended protocol for an additional 12 weeks, i.e. 24 weeks total, following review and signature of the EC approved patient's consent. Patients who completed **Part A** and did not discontinue the study due to a medical condition that might compromise safety assessments or for a PRN1008 related adverse event may be screened for entry under **Part B**.*

2. Pregnant or lactating women

3. ECG findings of QTc > 450 msec (males) or > 470 msec (females), poorly controlled atrial fibrillation (i.e. symptomatic patients or a ventricular rate above 100 beats/min on ECG), or other clinically significant abnormalities
4. A history of malignancy of any type, other than surgically excised non-melanoma skin cancers or in situ cervical cancer within 5 years before the day of dosing
5. Use of immunologic response modifiers with the following periods prior to Day 1: as concomitant therapy, other immunologic response modifiers not detailed in this exclusion apart from corticosteroids; *1 week*: cyclophosphamide; *4 weeks*: IVIG, Kinaret (anakinra) and Enbrel (etanercept); *12 weeks*: Remicade (infliximab), Humira (adalimumab), Simponi (golimumab), Orenzia (abatacept), Actemra (tocilizumab), Cimzia (certolizumab), Cosentyx (secukinumab), plasmapheresis; *6 months*: Rituxan/MabThera (rituximab), ofatumumab, any other anti-CD20 antibody, other long-acting biologics
6. More than 0.5 mg/kg of prednis(ol)one per day (“low dose corticosteroids”) within the two weeks prior to Day 1
7. Use of proton pump inhibitor drugs such as omeprazole and esomeprazole (it is acceptable to change patient to H2 receptor blocking drugs prior to the first dose of PRN1008)
8. Concomitant use of known strong-to-moderate inducers or inhibitors of CYP3A ([Appendix 2](#)) within 3 days or 5 half-lives (whichever is longer) of study drug dosing
9. Use of CYP3A-sensitive substrate drugs ([Appendix 3](#)) with a narrow therapeutic index within 3 days or 5 half-lives (whichever is longer) of study drug dosing including, but not limited to, alfentanil, astemizole, cisapride, cyclosporine, dihydroergotamine, ergotamine, fentanyl, pimozide, quinidine, sirolimus, tacrolimus, or terfenadine

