6.3.2 Concomitant Therapy

Not Permitted:

- Concomitant use of immunosuppressant medication, other than low-dose corticosteroids, unless rescue criteria ([Appendix 1](#)) are triggered.
- Concomitant use of known strong to moderate inducers or inhibitors of CYP3A ([Appendix 2](#)) within 14 days or 5 half-lives (whichever is longer) of dosing with PRN1008.
- Use of CYP3A-sensitive substrate drugs ([Appendix 3](#)) with a narrow therapeutic index within 14 days or 5 half-lives (whichever is longer) of PRN1008 dosing including, but not limited to, alfentanil, astemizole, cisapride, cyclosporine, dihydroergotamine, ergotamine, fentanyl, pimozone, quinidine, sirolimus, tacrolimus, or terfenadine.
- Proton pump inhibitors are not permitted. Esomeprazole was shown to reduce the exposure of PRN1008 by approximately 50%, presumably due to the effects of a lack of an acidic environment on tablet dissolution. Therefore, subjects who are on proton pump inhibitors should be changed to H2 receptor blocking drugs if possible or not enrolled in the study.

Permitted:

- The use of oral prednis(ol)one may be permitted in some circumstances. For admission to the study, doses of oral prednis(ol)one in the 2 weeks prior to Day 1 may be no higher than 0.5 mg/kg per day (inhaled and mucosal [for symptomatic treatment of oral lesions] corticosteroids are allowed). Where patients enter the study on low-dose corticosteroids, the regimen should be maintained for the initial 2 weeks of PRN1008 therapy. At the Day 15 review, a good clinical response to PRN1008 should allow the tapering of the corticosteroid to commence using the Werth taper ([Appendix 7](#)). At all times, the rescue criteria should be followed, as indicated ([Appendix 1](#)). In some circumstances, corticosteroids should be added or the dose increased, with or without cessation of PRN1008.
- Clinically relevant 3A substrate drugs (e.g., “sensitive substrate” listed in [Appendix 3](#)) should be managed by administering PRN1008 on a time schedule such that CYP 3A substrate drugs can be given 2 hours or more after PRN1008.
- H2 receptor blocking drugs and antacids are permitted provide PRN1008 is given at least 2 hours beforehand.
- Anticoagulation with warfarin should be monitored actively in the first weeks of PRN1008 therapy, as the combination has not been studied previously.

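### Section 2.4 says sensitive CYP3A substrates should be avoided, while the synopsis, 4.5.2 and 6.3.2 permit them from two hours after PRN1008, and no basis for the two hours is given

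*Protocol*

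**What the plan says.** Protocol Section 2.4 (Drug-Drug Interaction Potential) classes PRN1008 as a moderate CYP3A inhibitor and concludes that "sensitive CYP3A substrate drugs, particularly those with a narrow therapeutic index, should be avoided during treatment with PRN1008". It refers the reader to Appendix 2.

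Section 4.5.2 (Concomitant Medications) limits avoidance to a subset: "Narrow therapeutic index CYP3A substrate drugs should be avoided", with a reference to Appendix 3 and a general caution about other CYP3A-metabolised drugs. It then says that clinically relevant substrates, with the Appendix 3 sensitive substrates as its example, are to be timed so that "CYP3A substrate drugs can be given 2 hours or more after PRN1008". Section 6.3.2 repeats this under its Permitted heading: such drugs "should be managed by administering PRN1008 on a time schedule such that CYP 3A substrate drugs can be given 2 hours or more after PRN1008". The synopsis carries the same rule. Exclusion criterion 9 (Section 6.2) also reaches only substrates "with a narrow therapeutic index within 3 days or 5 half-lives (whichever is longer").

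On pharmacokinetics, Section 1.5.1 gives the time of maximum concentration "at therapeutic multiple doses of 1.5 to 2.0 hours", a delay for the tablet from 1.5 to about 2.5 hours with food, and a terminal half-life of about 3 to 4 hours. Section 4.5 allows dosing with or without food. On the size of the interaction, Section 2.4 reports: "When co-administered with midazolam, midazolam plasma exposures increased approximately 3-fold".

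**The concern.** These are safety instructions about co-medication, and they differ on whether a patient may take a given drug at all. A site working from Section 2.4 would withhold midazolam, simvastatin or quetiapine. A site working from Section 6.3.2 would allow them with spacing. Both could say that they followed the protocol, and a monitor would have no single standard for calling a deviation.

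The reference in Section 2.4 adds to the confusion. A reader who follows it finds a list of inhibitors and inducers instead of the substrates that the sentence is about.

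The second matter is the interval itself. The protocol sets a minimum of two hours without saying what that separation is meant to achieve or what evidence supports it, and its own figures put two hours close to the time of peak PRN1008 concentration.

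**Working it through.** **1. The instructions side by side**

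- Section 2.4: avoid sensitive substrates as a class. The word particularly singles out the narrow-therapeutic-index drugs without confining the instruction to them. Reference: Appendix 2.
- Synopsis, 4.5.2 and 6.3.2: avoid the narrow-therapeutic-index drugs; give other sensitive substrates two hours or more after PRN1008. Reference: Appendix 3.
- Exclusion 9: narrow-therapeutic-index substrates only. Reference: Appendix 3.

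The narrow-therapeutic-index drugs are treated alike throughout. The conflict concerns the remaining sensitive substrates.

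**2. How many listed drugs are affected**

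- Drugs in the sensitive-substrate column of Appendix 3: 30.
- Also in its narrow-therapeutic-index column, so avoided under either rule: alfentanil and sirolimus, 2.
- Also listed singly in Appendix 2 as strong or moderate inhibitors, so barred on other grounds: aprepitant, conivaptan, indinavir and saquinavir, 4.
- Listed in Appendix 2 only in combination with ritonavir: darunavir and lopinavir, 2.

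30 − 2 − 4 = 24 drugs get different answers, or 24 − 2 = 22 if the two ritonavir combinations are counted as barred. This uses the two appendices only; other eligibility rules may remove a few more.

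**3. The appendix reference**

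Appendix 2 is headed as strong and moderate CYP3A inhibitors and inducers. The substrates are in Appendix 3.

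**4. The two-hour minimum against the protocol's own figures**

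- Time to peak at therapeutic multiple doses, 1.5 to 2.0 hours: two hours is the upper end of the range.
- Tablet without food, 1.5 hours: 2.0 − 1.5 = 0.5 hours after the peak.
- Tablet with food, about 2.5 hours: 2.5 − 2.0 = 0.5 hours before the peak.
- Half-life, 3 to 4 hours: 2/4 = 0.5 to 2/3 = 0.67 of one half-life.
- Section 11.3.1 defines the Day 1 PK outcome as the concentration at about the time of maximum concentration. The Appendix 4 footnotes time the Day 1 post-dose sample at 2 hours, plus or minus 15 minutes.

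The earliest time that the rule permits is therefore within half an hour of every stated time to peak, and it is the time at which the trial itself samples for the peak.

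**5. Evidence for the interval**

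The one interaction study described, PRN1008-002, gave PRN1008 and midazolam simultaneously. Neither the protocol nor the SAPs report a study with separated dosing or give a reason for two hours.

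**The case against.** The strongest reply is that the operative text is consistent. The synopsis, 4.5.2 and 6.3.2 state one rule, exclusion 9 agrees with it on scope, and 4.5.2 adds a general caution. The outlier is one sentence in a rationale section, which may be a leftover. This makes it less likely that sites diverge in practice. It does not remove the conflict, because the sentence in 2.4 is worded as an instruction and nothing says which section prevails.

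On the interval, several objections stand:

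- Two hours is a minimum, not the prescribed time, and the time to peak is given as a range.
- Nothing in the documents says that the spacing is meant to avoid the plasma peak. If the aim is to limit inhibition in the gut wall, the plasma peak may not be the relevant measure.
- The threefold midazolam effect followed single 600 mg doses of the liquid (Section 1.4.1). With tablet exposure at about 70% of an equal liquid dose (Section 4.5.1), that corresponds to about 600/0.70 ≈ 857 mg of tablet, above the 400 to 600 mg taken per dose under the main dosing schedule. The effect at trial doses could differ.
- Section 2.4 refers to the Investigator's Brochure for more detail, and a rationale may be there.

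A reader might infer that the two-hour rule contradicts the protocol's PK figures, or might use a simple model to put a percentage on the plasma level at two hours. The documents support neither. The first assumes a purpose that the protocol does not state. For the second, simple linear elimination with a 3 to 4 hour half-life and 12-hourly dosing gives an accumulation ratio of 1/(1 − 2^(−12/3)) = 1.07 to 1/(1 − 2^(−12/4)) = 1.14, against the 1.8 that Section 1.5.1 reports for 300 mg of the liquid twice daily. Such a model does not fit the reported kinetics well enough to quote percentages from it.

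**Conclusion.** The contradiction stands on the wording alone. Section 2.4 and the other three places give incompatible instructions for 22 to 24 of 30 listed drugs, and the appendix reference in 2.4 is wrong. No assumption is needed beyond reading both texts as directions to sites.

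The finding on the interval is narrower. The two-hour minimum falls at or near the stated times to peak, and these documents give no basis for it. That is a gap in justification. It does not show that the interval is unsafe, and it applies only to what the protocol and SAPs contain.

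Because Appendix 3 includes budesonide and fluticasone, and Section 6.3.2 allows inhaled and mucosal steroids, a reader might also infer that hidden systemic steroid exposure affects the endpoints defined without corticosteroids. The documents show neither use of these drugs nor any resulting exposure, and both SAPs exclude topical steroid from those endpoints by explicit definition. That inference should not be rested on this point.

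**What to change.** Reconcile Section 2.4 with the synopsis, 4.5.2 and 6.3.2 so that one instruction applies to the Appendix 3 sensitive substrates, and change the reference in 2.4 from Appendix 2 to Appendix 3. If a time separation is kept, the sponsor should state its basis against the time to peak, with and without food, and the half-life, citing the Investigator's Brochure if the rationale is there. Which instruction applies, and any interval, are for the sponsor's clinical pharmacology and safety staff; nothing is proposed here.

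The cost is a wording amendment with the submissions required by Section 14.4, a note to sites, and a check of current patients' co-medication against the reconciled rule. No analysis or sample size changes.
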